7.2.2 Reporting of Pregnancy and Lactation to the Sponsor

Although pregnancy and lactation are not considered adverse events, it is the responsibility of investigators or their designees to report any pregnancy or lactation in a subject (spontaneously reported to them) that occurs during the trial.

Pregnancies and lactations that occur after the consent form is signed but before treatment allocation/randomization must be reported by the investigator if they cause the subject to be excluded from the trial, or are the result of a protocol-specified intervention, including but not limited to washout or discontinuation of usual therapy, diet, placebo treatment or a procedure. Pregnancies and lactations that occur from the time of treatment allocation/randomization through 120 days following cessation of Sponsor's product or 30 days following cessation of treatment if the subject initiates new anticancer therapy, whichever is earlier, must be reported by the investigator. All reported pregnancies must be followed to the completion/termination of the pregnancy. Pregnancy outcomes of spontaneous abortion, missed abortion, benign hydatidiform mole, blighted ovum, fetal death, intrauterine death, miscarriage and stillbirth must be reported as serious events (Important Medical Events). If the pregnancy continues to term, the outcome (health of infant) must also be reported.

Such events must be reported within 24 hours to the Sponsor either by electronic media or paper. Electronic reporting procedures can be found in the EDC data entry guidelines. Paper reporting procedures can be found in the Investigator Trial File Binder (or equivalent).

7.2.3 Immediate Reporting of Adverse Events to the Sponsor

7.2.3.1 Serious Adverse Events

A serious adverse event is any adverse event occurring at any dose or during any use of Sponsor's product that:

- Results in death;
- Is life threatening;
- Results in persistent or significant disability/incapacity;
- Results in or prolongs an existing inpatient hospitalization;
- Is a congenital anomaly/birth defect;
- Is an other important medical event.

Note: In addition to the above criteria, adverse events meeting either of the below criteria, although not serious per ICH definition, are reportable to the Sponsor in the same timeframe as SAEs to meet certain local requirements. Therefore, these events are considered serious by the Sponsor for collection purposes.

- Is a new cancer (that is not a condition of the study);
- Is associated with an overdose.

Refer to [Table 15](#) for additional details regarding each of the above criteria.

For the time period beginning when the consent form is signed until treatment allocation/randomization, any serious adverse event, or follow up to a serious adverse event, including death due to any cause other than progression of the cancer under study (reference Section 7.2.3.3 for additional details), that occurs to any subject must be reported within 24 hours to the Sponsor if it causes the subject to be excluded from the trial, or is the result of a protocol-specified intervention, including but not limited to washout or discontinuation of usual therapy, diet, placebo treatment or a procedure.

For the time period beginning at treatment allocation/randomization through 90 days following cessation of treatment or 30 days following cessation of treatment if the subject initiates new anticancer therapy, whichever is earlier, any serious adverse event, or follow up to a serious adverse event, including death due to any cause other than progression of the cancer under study (reference Section 7.2.3.3 for additional details), whether or not related to the Sponsor's product, must be reported within 24 hours to the Sponsor either by electronic media or paper. Electronic reporting procedures can be found in the EDC data entry guidelines. Paper reporting procedures can be found in the Investigator Trial File Binder (or equivalent).

Additionally, any serious adverse event, considered by an investigator who is a qualified physician to be related to the Sponsor's product that is brought to the attention of the investigator at any time following consent through the end of the specified safety follow-up period specified in the paragraph above, or at any time outside of the time period specified in the previous paragraph also must be reported immediately to the Sponsor.

All subjects with serious adverse events must be followed up for outcome.

7.2.3.2 Events of Clinical Interest

Selected non-serious and serious adverse events are also known as Events of Clinical Interest (ECI) and must be reported to the Sponsor.

For the time period beginning when the consent form is signed until treatment allocation/randomization, any ECI, or follow up to an ECI, that occurs to any subject must be reported within 24 hours to the Sponsor if it causes the subject to be excluded from the trial, or is the result of a protocol-specified intervention, including but not limited to washout or discontinuation of usual therapy, diet, placebo treatment or a procedure.

For the time period beginning at treatment allocation/randomization through 30 days following cessation of treatment, any ECI, or follow up to an ECI, whether or not related to the Sponsor's product, must be reported within 24 hours to the Sponsor, either by electronic media or paper. Electronic reporting procedures can be found in the EDC data entry guidelines. Paper reporting procedures can be found in the Investigator Trial File Binder (or equivalent).

Events of clinical interest for this trial include:

1. an overdose of Sponsor's product, as defined in Section 7.2.1 - Definition of an Overdose for This Protocol and Reporting of Overdose to the Sponsor, that is not associated with clinical symptoms or abnormal laboratory results.

2. an elevated AST or ALT lab value that is greater than or equal to 3X the upper limit of normal and an elevated total bilirubin lab value that is greater than or equal to 2X the upper limit of normal and, at the same time, an alkaline phosphatase lab value that is less than 2X the upper limit of normal, as determined by way of protocol-specified laboratory testing or unscheduled laboratory testing.*

*Note: These criteria are based upon available regulatory guidance documents. The purpose of the criteria is to specify a threshold of abnormal hepatic tests that may require an additional evaluation for an underlying etiology. The trial site guidance for assessment and follow up of these criteria can be found in the Investigator Trial File Binder (or equivalent).

3. The following events should also be reported as an ECI if they occur after the start of treatment in the axitinib/ pembrolizumab combination arm:
 - a. events with ALT and/or AST > 5xULN
 - b. events with ALT and/or AST > 3xULN concurrently with total bilirubin $\geq 2xULN$

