Based on the existing data from clinical trials, ALT/AST elevations have been observed in advanced cancer patients who received axitinib or pembrolizumab monotherapy treatment. In the Phase 3 study that compared axitinib versus sorafenib in treatment-naïve advanced RCC patients [15], laboratory data showed that the rate of ALT elevation was 40.4% for all grade, 29.8% for Grade 1, 6.7% for Grade 2, 3.9% for Grade 3, and zero for Grade 4. The AE data showed that reported ALT elevation regardless of causality was 10.6% for all grade, 4.8% for Grade 1, 2.6% for Grade 2, 3.2% for Grade 3, and zero for Grade 4. Similar results were observed for AST [unpublished data provided by Pfizer].

Based on data from 2799 subjects with either advanced melanoma or NSCLC treated with pembrolizumab monotherapy, the incidence of immune-mediated hepatitis was 0.7% for all grade, 0.4% for Grade 3, and no Grade 4 or 5 events [Pembrolizumab IB]. In the updated data from an ongoing Phase 1/2 study of axitinib plus pembrolizumab in treatment-naïve advanced RCC, 4 out of 52 subjects had Grade 3 and another 4 had Grade 2 treatment-related ALT/AST elevations or hepatic dysfunction.

Differentiation of whether ALT/AST elevations are attributable to axitinib or pembrolizumab or both may be challenging, as no specific clinical picture or laboratory markers are available. In addition, alternative causes (e.g., viral hepatitis and other severe infections, liver metastasis, ischemia, alcohol intake, etc.) should be excluded before more definitively concluding the attribution of ALT/AST elevation by the study drugs.

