For assessing drug-induced liver injury (DILI), the Roussel Uclaf Causality Assessment Method (RUCAM) can be used as a valid tool in which factors like time to onset of ALT/AST elevation, response to drug dechallenge, response to drug rechallenge, evaluation of alternative causes etc. are collectively evaluated and scored to determine the possibility of attribution to ALT/AST elevation [54]. For axitinib, early-onset, prompt recovery from ALT/AST elevation in response to axitinib interruption without confounding by corticosteroid treatment, suggests the event is likely associated with axitinib after excluding other alternative explanations). A positive rechallenge, i.e., ALT/AST recurrence following retreatment will provide further support for its attribution. The determination of immune-related hepatitis mostly relies on the exclusion of other causes including axitinib. If the initial ALT/AST elevation does not respond rapidly to axitinib interruption but responds to subsequent corticosteroid treatment, it suggests a potential for immune-mediated hepatitis by pembrolizumab. It should be borne in mind that not all immune-mediated hepatitis will respond to corticosteroid treatment.

Guidelines on causality evaluation and management for ALT/AST elevations of > 3xULN during axitinib / pembrolizumab combination treatment are outlined in the following:

1. **Promptly interrupt both study drugs and any other suspected concomitant medications.** Note, concomitant medications include over-the-counter (OTC) and herbal medications and supplements.
2. **Adequately monitor liver enzymes and liver function changes** - Liver enzyme tests should include ALT, AST, and ALP; liver function tests should include total bilirubin, and PT or INR. Bilirubin fractionation should be performed if total bilirubin is $\geq 2xULN$ or is clinically significant as elevated conjugated bilirubin (i.e., direct bilirubin) reflects liver dysfunction. Liver enzyme tests and liver function tests will be referred, collectively, as liver tests for the rest of this section.
 - a. Repeat liver tests within 24 to 72 hours to confirm the initial observation.
 - b. Continue to monitor liver tests twice weekly, while evaluating other causes, until ALT/AST values are trending down (>10% decrease between sequential assessments) and then monitored weekly until recovered to $\leq 2xULN$ or values are back to baseline.

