
Scenario 4: ALT/AST > 10 × ULN without clinically significant signs of hepatic dysfunction
 
Consultation with Sponsor medical monitor is required prior to rechallenge
	
 • If initial event is likely to be immune-mediated by pembrolizumab: 
 ○ discontinue pembrolizumab and rechallenge with axitinib as monotherapy • If initial event is likely related to axitinib and unlikely due to pembrolizumab: 
 ○ Rechallenge with pembrolizumab monotherapy • If event is potentially related to a contribution of both drugs (such as upfront steroid use with improvement along with axitinib interruption), subject may be rechallenged with axitinib at reduced dose: 
 ○ If no recurrence, continue with axitinib monotherapy ○ If ALT/AST elevation recurs, discontinue axitinib and may be rechallenged with pembrolizumab • Permanently discontinue pembrolizumab if ALT/AST recurrence is >5× ULN or interrupt pembrolizumab if ALT/AST recurrence is >3 to 5× ULN after its rechallenge and manage per Section 5.2.2.1. • Permanently discontinue axitinib if ALT/AST recurrence is >5× ULN or interrupt axitinib if ALT/AST recurrence is >3 to 5× ULN and rechallenge with reduced dose.

Note: 1. Subject should have weekly monitoring with liver tests (i.e., liver enzyme and function tests) for 2-3 weeks after each drug rechallenge. 2. If both study drugs are discontinued due to a hepatic event, subjects should be monitored until AE resolution as per protocol and continue imaging and survival follow-up as per protocol. 3. Events under Scenario 1, 3, and 4 must be reported to the Sponsor as Events of Clinical Interest (see Section 7.2.3.2 for details). 4. Liver tests include liver enzyme (ALT, AST, and ALP) and liver function (bilirubin and PT/INR) tests.
 
Abbreviations: ALP = alkaline phosphatase; ALT = alanine aminotransferase; AST = aspartate aminotransferase; INR = international normalized ratio; PT = prothrombin time.
	

5.2.2.4 Dose Modification Guidelines for Adverse Events Potentially Associated with Sunitinib Treatment

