	Urine protein ≥ 3 g/24 hr or UPC ≥ 3	Hold until urine protein is < 3 g/24 hr or UPC <3. Restart with 1 dose level lower Permanently discontinue if urine protein cannot reduce to < 3 g/24 hr or UPC <3 after dose reduced to 25 mg daily
Prolongation of QTc Interval:	480 < QTc < 500 msec	Continue study treatment; monitor as clinically indicated.
	QTc ≥ 500 msec	Permanently discontinue and follow-up per protocol.
Diarrhea/Colitis	Grade 1-2	Continue at the same dose level
	Grade 3	Continue and dose reduce by 1 dose level Follow the guidelines as in non-hematologic toxicities
	Grade 4	Follow the guidelines as in non-hematologic toxicities
Hemorrhage /Bleeding: Investigate and document underlying etiology of the bleeding	Grade 1	For hemoptysis, interrupt study treatment and evaluate underlying causes. Resume at the discretion of the investigator. For other Grade 1 hemorrhage/bleeding events, continue at the current dose; monitor as clinically indicated.
	Grade 2	For pulmonary or GI bleed (other than hemorrhoidal bleeding), Permanently discontinue and follow-up per protocol. For other Grade 2 hemorrhage/bleeding events, interrupt study treatment until the AE resolved to \leq Grade 1. Restart at 1 dose level lower
	Grade 3 or 4	Permanently discontinue and follow-up per protocol.
Hyperthyroidism	Grades 1-2	Continue at the same dose level
	Grade 3	Grade 3 toxicities controlled with symptomatic medications, or Grade 3 asymptomatic biochemistry (other than abnormal liver tests) laboratory abnormalities: may continue at the same dose level or reduce by one dose level per Investigator judgment
	Grade 4	Hold until recovery to Grade ≤ 1 or BL. Restart at 1 dose level lower.
Hypothyroidism	All grades	Dose can be continued while thyroid replacement therapy is instituted
Isolated AST/ ALT or bilirubin elevation	Grade 1	Continue at the same dose level
	Grade 2	Hold until recovery to Grade ≤ 1 or BL. Restart at same dose level.
	Grade 3 or 4	Hold until recovery to Grade ≤ 1 or BL. Restart at 1 dose level lower.
	ALT/AST >3xULN concurrent with total bilirubin > 2xULN (excluding Gilbert syndrome)	Permanently discontinue and perform virology and serology tests to evaluate the causes

Toxicity	NCI CTCAE Grade	Sunitinib
Non-hematologic Toxicities, Laboratory Abnormalities and/or Other Drug Related Toxicities suspected to be contributed to sunitinib	Grade 1 - 2	Continue at the same dose level

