8.6.2 Statistical Methods for Safety Analyses

Safety and tolerability will be assessed by clinical review of all relevant parameters including AEs, laboratory tests, and vital signs.

Tiered Approach

The analysis of safety results will follow a tiered approach (Table 19). The tiers differ with respect to the analyses that will be performed. For this protocol, there are no Tier 1 events.

Tier 2 parameters will be assessed via point estimates with 95% CIs provided for between-group comparisons; only point estimates by treatment group are provided for Tier 3 safety parameters.

Adverse events (specific terms as well as system organ class terms) will be classified as belonging to "Tier 2" or "Tier 3", based on the number of events observed. Membership in Tier 2 requires that at least 10% of the subjects in any treatment group exhibit the event; all other AEs and predefined limits of change will belong to Tier 3.

The threshold of at least 10% of subjects with events was chosen for Tier 2 event because the incidence rate would allow meaningful statistical assessments; events reported in less frequent than 10% of subjects would obscure the assessment of overall safety profile and add little to the meaningful interpretation. Because many 95% CIs may be provided without adjustment for multiplicity, the confidence intervals should be regarded as a helpful descriptive measure to be used in review, not a formal method for assessing the statistical significance of the between-group differences in AEs and predefined limits of change.

Continuous measures such as changes from baseline in laboratory values and vital signs that are not pre-specified as Tier 1 safety parameters will be considered Tier 3 safety parameters. Summary statistics for baseline, on-treatment, and change from baseline values will be provided by treatment group in table format.

In addition, the broad clinical and laboratory AE categories consisting of the percentage of subjects with Grade 3-5 AE (incidence $\geq 5\%$ of subjects in one of the treatment groups) and any SAE (incidence $\geq 5\%$ of subjects in one of the treatment groups) will be considered Tier 2 endpoints.

The threshold of at least 5% of subjects with events was chosen for Tier 2 Grade 3-5 AEs and SAEs because the incidence rate would allow meaningful statistical assessments; those AEs are expected to happen less frequent than specific AEs/SOCs but important for overall safety profile assessment.

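### Liver-enzyme rises are prompted for and retested more closely in the combination arm, and the SAP plans no between-arm interval on graded laboratory values to check the hepatic AE comparison

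*Combined protocol and SAP*

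**What the plan says.** **ECI reporting (Section 7.2.3.2).** Item 2 has no arm restriction. It starts from "an elevated AST or ALT lab value that is greater than or equal to 3X the upper limit of normal" and also needs total bilirubin at or above 2xULN with alkaline phosphatase below 2xULN. Item 3 is for one arm: "The following events should also be reported as an ECI if they occur after the start of treatment in the axitinib/ pembrolizumab combination arm". Its two limbs are "events with ALT and/or AST > 5xULN", and ALT/AST above 3xULN together with bilirubin at or above 2xULN. Note 3 to Table 10, which covers the same arm, repeats the duty: "Events under Scenario 1, 3, and 4 must be reported to the Sponsor as Events of Clinical Interest".

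**Triggered testing.** For the combination, Section 5.2.2.3.1 sets a repeat test 24 to 72 hours after ALT/AST exceeds 3xULN, then "Continue to monitor liver tests twice weekly, while evaluating other causes, until ALT/AST values are trending down", then weekly until recovery. Table 10 adds weekly tests for 2 to 3 weeks after each rechallenge. Table 11, for sunitinib, gives no test interval. Its row on isolated AST/ALT or bilirubin elevation says, for Grade 3 or 4, "Hold until recovery to Grade ≤ 1 or BL. Restart at 1 dose level lower". It also calls for virology and serology when ALT/AST exceeds 3xULN with bilirubin above 2xULN.

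**Scheduled chemistry.** Footnote u of Section 6.1 (combination) sets Day 1 of every 21-day cycle from Cycle 2. Footnote u of Section 6.2 (sunitinib, 42-day cycles) sets Day 29 of Cycles 1 to 3, Day 1 of Cycles 2 and 3, and Day 1 of each cycle from Cycle 4.

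**AE collection.** Section 7.2 counts abnormal laboratory findings as possible AEs and requires all AEs from randomization to 30 days after treatment, in both arms. Section 7.2.4 requires each change of grade within an episode to be recorded.

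**Analysis (Section 8.6.2, Table 19).** For specific AE terms, "Membership in Tier 2 requires that at least 10% of the subjects in any treatment group exhibit the event"; for Grade 3-5 and serious AEs the threshold is 5%. Tier 2 events get a between-arm 95% CI. Laboratory changes from baseline and predefined limits of change are Tier 3, summarized by arm with no interval.

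**The concern.** Comparing safety between arms is secondary objective 3, and liver toxicity is singled out for the combination by a section of its own. The trial is open-label, so whether a laboratory value becomes an AE record depends partly on an investigator who knows the treatment.

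Three features could each raise the combination's recorded hepatic AEs relative to sunitinib's: a numeric reporting prompt, timed retesting after a first elevation, and more frequent scheduled chemistry later on. Because each change of grade is recorded, denser retesting can raise the recorded maximum grade and find more recurrences. The measure that depends least on reporting prompts, the graded laboratory value, gets no between-arm interval.

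The risk runs both ways. An excess on the combination could be exaggerated, or a genuine excess could be dismissed as an artefact of closer surveillance. AE terms alone cannot settle which.

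**Working it through.** The plan states no figure for this point, so there is none to reproduce.

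**1. Count scheduled post-baseline chemistry draws** from the two footnotes u, assuming uninterrupted treatment.
- Combination: weeks 3, 6, 9, 12, 15, 18, then every 3 weeks.
- Sunitinib: weeks 4, 6, 10, 12, 16, 18, then every 6 weeks.

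| Through week | Combination | Sunitinib |
|---|---|---|
| 12 | 4 | 4 |
| 18 | 6 | 6 |
| 24 | 8 | 7 |
| 54 | 18 | 12 |
| 104 | 34 | 20 |

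From Cycle 4 every scheduled on-treatment sunitinib draw falls on Day 1, after the two scheduled weeks off drug. Axitinib is taken continuously.

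**2. Effect on first detection after Week 18.** An elevation lasting L days with random onset meets a scheduled draw with probability min(1, L/interval). The duration is an assumption.
- L = 14: 14/21 = 0.67 against 14/42 = 0.33.
- L = 21: 21/21 = 1.0 against 21/42 = 0.5.

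Triggered tests start only after a first elevation is found. They can affect maximum grade and recurrence, not first detection.

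**3. What the documents show about capture at the ECI threshold.** Table 10 equates above 5xULN with Grade 3 or 4. For the first-line axitinib study, Section 5.2.2.3.1 gives laboratory Grade 3 ALT elevation as 3.9%, and by AE report "reported ALT elevation regardless of causality was 10.6% for all grade, 4.8% for Grade 1, 2.6% for Grade 2, 3.2% for Grade 3". The Grade 3 ratio is 3.2/3.9 = 0.82. In the Phase 1b combination study, Grade 3 ALT was 3 of 52 by AE (Table 2) and 2 of 52 by laboratory (Table 3), so there was no shortfall. Neither source gives capture on sunitinib.

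**4. Illustration of size.** Assume the same true Grade 3+ rate p in both arms, full AE capture on the combination and capture c on sunitinib. The artefactual difference is p(1 − c). The 95% half-width is 1.96 × √[p(1 − p)/n + pc(1 − pc)/n], with n about 430 per arm (861/2).

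| True rate p | c = 1.00 | c = 0.82 | c = 0.60 |
|---|---|---|---|
| 3.9% | 0 | 0.7 points (± 2.5) | 1.6 points (± 2.3) |
| 8% | 0 | 1.4 points (± 3.5) | 3.2 points (± 3.3) |
| 15% | 0 | 2.7 points (± 4.6) | 6.0 points (± 4.3) |

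For example, 0.039 × 0.18 = 0.0070 and 0.15 × 0.18 = 0.027. Every value of c is an assumption. The table covers incomplete reporting only, not the testing-frequency effect in step 2.

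**The case against.** The case on the other side is substantial.

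- **ECI status sets reporting speed, not collection.** ECIs are a subset of AEs that both arms must report. ECI is not a tier or endpoint in Section 8.6.2, and item 2 covers both arms. This stands. What remains is that an explicit numeric threshold may prompt recording that is otherwise left to judgment.
- **Sunitinib patients are retested too.** Table 11's hold rule presupposes a repeat value, and non-serious AEs are followed for outcome in both arms. This stands, but no interval is given.
- **The intervals are declared descriptive, and laboratory data are summarized by arm.** Both are true. The summaries are of change from baseline and predefined limits. The plan does not say they are CTCAE-graded, and they carry no between-arm interval.
- **Closer surveillance has a stated basis.** Section 5.2.2.3.1 reports 4 of 52 patients with Grade 3 and 4 of 52 with Grade 2 treatment-related hepatic events on the combination, and Section 4.2.2.2 describes sunitinib's safety profile as well characterized. That explains the surveillance but does not make the resulting AE counts comparable.

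A reader might go further and infer that the hepatic AE comparison is biased against the combination, citing the gap between 40.4% (laboratory) and 10.6% (AE report) for all-grade ALT elevation on axitinib. The documents do not support this. Most of that gap lies below 5xULN. The Grade 3 figures differ by 0.7 points, about one patient if the denominator is near 192 (0.007 × 192 = 1.3). They concern axitinib, and the Phase 1b tables show the reverse order.

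**Conclusion.** The asymmetry is documented: the ECI prompt above 5xULN and the timed retests are written for the combination only, and scheduled chemistry after Week 18 is every 3 weeks against every 6. It creates a risk that hepatic AE rates and maximum grades are inflated in the combination relative to sunitinib; it does not establish that they are.

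The size is unknown. It is zero under equal capture and about 0.7 to 2.7 points under 82% sunitinib capture at true Grade 3+ rates of 3.9% to 15%, within the sampling half-widths of 2.5 to 4.6 points. That range rests on equal true rates, full capture on the combination and a capture figure borrowed from axitinib.

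Nor should a reader conclude that true risk and ascertainment could never be separated. Laboratory values are collected in both arms; what is missing is a planned comparison that uses them on matched draws. Adding it is a worthwhile, inexpensive improvement.

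**What to change.** **1. Main change, in Section 8.6.2 or the sSAP.** Add a supportive between-arm comparison, with a Miettinen and Nurminen 95% CI, of maximum CTCAE-graded ALT/AST from scheduled laboratory values through Week 18, where each arm has six draws. Exclude tests triggered by Section 5.2.2.3.1. Using all scheduled values instead would carry the 3- versus 6-week imbalance into the comparison. Keep the AE-term analyses as planned, show all laboratory values descriptively (including triggered and later ones), and state the unequal testing as a limitation.

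The cost is a small amount of extra analysis on data already collected. The comparison omits late-onset elevations and triggered peak values. It equalizes the number of draws rather than their exact timing: three of the six sunitinib draws (weeks 6, 12 and 18) follow the scheduled two weeks off drug.

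**2. Secondary change, in Section 7.2.3.2.** Apply item 3 reporting to both arms, with note 3 of Table 10 kept consistent, or state why it is restricted. This matters less because all 861 subjects are already randomized. A change now would alter sunitinib reporting partway through unless earlier values were queried retrospectively.

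Neither change alters or proposes any liver-management rule.
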